7.4 Islet Transplant and Study Treatment Visits

Blood group compatible and crossmatch negative subjects selected for islet transplantation will be invited to the study center upon determination of preliminary islet suitability based on count and quality. After preliminary testing detailed in Appendix 1, SOE (- 2 days relative to transplant), the subject will be admitted for induction therapy with rabbit ATG. This can be administered via central vein catheter, PICC line, or peripheral IV⁹⁸. A period of in vitro culture is considered essential to the protocol because of the use of rabbit ATG induction

Immunosuppression may cause a transient cytokine release associated with the initial doses. The period of in vitro culture will allow time for any cytokine release to dissipate after treatment of the subject with ATG and will also permit time for microbiological and potency assessment of the islet preparation prior to transplant.

Once islets have been examined at the end of the culture period but prior to final release testing, the pharmacy will compile the needed dose to allow the infusion to be completed within three hours of reconstitution. GLASSIA will be infused within three hours before the intended start of the islet infusion but after the final release criteria confirm islet suitability.

Following induction therapy, subjects will remain on a calcineurin-based maintenance immunosuppression regimen. This can consist of tacrolimus alone or in conjunction with sirolimus, mycophenolate mofetil, myfortic, or azathioprine; or cyclosporine in conjunction with sirolimus,

mycophenolate mofetil, or myfortic. Subjects on CsA alone will be excluded. Up to 10 mg/day of steroids are also acceptable in conjunction with either regimen. For subjects on tacrolimus plus sirolimus, combined levels (*i.e.*, tacrolimus plus sirolimus) should target 12-20 (tacrolimus target level 3-10 ng/mL and sirolimus target level 3-15). For subjects receiving tacrolimus plus mycophenolate mofetil, tacrolimus levels should target 6-10 and the mycophenolate mofetil dose should target 1-2 gm/day. Mycophenolate sodium is an acceptable alternative to mycophenolate mofetil. For subjects on CsA plus either sirolimus, mycophenolate mofetil, or myfortic, combined trough levels should target 100-300 ng/mL or the 2 hour level should target 350-500 ng/mL for the first 3 months post-transplant and 200-350 ng/mL thereafter. Drug target levels can be adjusted at the discretion of the treating transplant physician based on subject care needs including graft rejection, drug-related graft injury, drug-related side effects, or infection.

7.5 Follow-up Visits

Islet transplant recipients will undergo a minimum 36-month follow-up period following the last islet transplant to include time points relevant to the initial transplant. The timing of all follow-up assessments will “reset” with additional transplants; *i.e.*, the day of the 2nd transplant becomes day 0 and the subsequent assessments are conducted in relation to this day. Please refer to the Appendix 1, SOE, for the clinical time points of specific follow-up study procedures.

7.6 Criteria and Timing for Subsequent Islet Transplants

Subjects who do not meet criteria for a subsequent transplant will enter a reduced follow-up schedule (Appendix 2).

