TAT	Thrombin-antithrombin
TB	Tuberculosis
TCAE	Terminology Criteria for Adverse Events
Tid	Three times daily
TNF	Tumor Necrosis Factor
ULN	Upper Limit of Normal
UNOS	United Network of Organ Sharing
WHO	World Health Organization
y.o.	Years old

Study Definitions

Full graft function: Islet transplant recipients will be considered to have full islet graft function if they are insulin independent (as defined below).

Graft failure: Islet allograft failure will be defined as absence of insulin production by transplanted islets, as evidenced by c-peptide < 0.3 ng/mL. This will be determined by (1) c-peptide < 0.3 ng/mL on random testing, followed by (2) c-peptide < 0.3 ng/mL at baseline, and at 60 and 90 minutes after MMTT. Participants with graft failure do not need to complete the day 75 metabolic assessments.

Insulin-independent: Islet transplant recipients will be considered insulin-independent with full islet graft function if they are able to titrate off insulin therapy for at least 1 week and all of the following criteria are met:

- One HbA1c level, one fasting serum glucose level, and a Mixed Meal Tolerance Test are documented within the visit window (e.g. 70-80 days at Day 75) and 7 consecutive days of blood sugar and insulin readings are documented within ± 7 days of the visit window (e.g. 63-87 days at Day 75);
- HbA1c $\leq 6.5\%$ or a $\geq 2.5\%$ decrease from baseline (within 91 days prior to transplant);
- Fasting capillary glucose level should not exceed 140 mg/dL more than three times in 7 consecutive days (fasting is defined as 1st blood sugar reading of the day not noted as post-prandial or bedtime);
- Post-prandial serum glucose ≤ 180 mg/dL at 90 minutes during the MMTT;
- Fasting serum glucose level ≤ 126 mg/dL; if the fasting serum glucose level is > 126 mg/dL, it must be confirmed in an additional one out of two measurements;
- At least one MMTT fasting or stimulated c-peptide ≥ 0.5 ng/mL.

Insulin dependent: Islet transplant recipients who do not meet the criteria for insulin independence will be considered insulin-dependent.

Intensive diabetes management: Self-monitoring of glucose values no less than a mean of three times each day averaged over each week and by the administration of three or more insulin injections each day or insulin pump therapy.

Partial graft function: Islet transplant recipients who do not meet criteria for insulin independence, but have either a basal or stimulated c-peptide level ≥ 0.3 ng/mL (0.1 nmol/L).

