5.8.2 Modification of Standard Immunosuppression

ISLETS ARE UNSUITABLE

Should an islet product become unsuitable for transplantation subsequent to induction immunosuppression, the subject will remain on maintenance therapy required for their renal transplant. This will provide sufficient time for organ procurement, islet isolation, and infusion of an islet product without any additional induction treatment to the recipient. An emergency request will be placed through UNOS that the next available pancreas for islet transplantation is directed to the selected manufacturing site. When an organ becomes available, investigators should defer to the MOP to determine the amount and type of induction immunosuppression that will be administered at the time of islet transplant.

GRAFT FAILURE

Subjects who experience islet graft failure will be maintained on their current immunosuppressive regimen for their renal graft as long as a subsequent islet transplant is possible. If/when it is determined that a subject will not receive a subsequent islet transplant, the subject will move to the reduced follow-up schedule.

ALLERGIC REACTION TO ATG

If a subject demonstrates an allergic reaction to thymoglobulin that results in cancellation of the initial transplant and the investigators feel that future use of the drug in the subject is contraindicated, the steps outlined should be followed. Once another organ becomes available, the subject will receive the alternate induction immunosuppressive regimen outlined in this protocol.

INTOLERANCE OF PROTOCOL MEDICATIONS

In the event that protocol-regulated concomitant medications are not tolerated, the subject will continue taking the immunosuppressive therapy in order to protect the islet and renal grafts. In the event that the immunosuppression regimen is not tolerated, the site PI may elect to prescribe an alternative immunosuppression regimen. The intent would be for the alternative regimen to be temporary in nature.

where possible and any such decision made with the primary interest of maintaining the function of the renal allograft. Any non-protocol directed study treatment modification that the site PI determines is necessary should be reported as a protocol deviation.

RABBIT ANTI-THYMOCYTE GLOBULIN-INDUCED ANAPHYLAXIS

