5.8.3 Premature Discontinuation of Study Treatment (Transition to “Reduced Follow- up” Treatment)

Study treatment will begin at the time of the first dose of induction antibody therapy for an islet transplant. Study treatment may be prematurely discontinued for any subject for any of the following reasons:

- The subject is unwilling or unable to comply with the protocol.
- The investigator believes that the study treatment is no longer in the best interest of the subject.
- The renal allograft is lost and the subject elects to terminate chronic immunosuppression.
- Graft Failure: See Study Definitions and Section 5.8.2.
- An unexpected related SAE. The agent(s) to which the event is attributed will be discontinued.

Subjects who prematurely discontinue study treatment will remain in the study until normal termination, for the purpose of monitoring safety and efficacy parameters and will enter the reduced follow-up schedule outlined in Appendix 2. Data from these subjects will be used in the intent-to-treat analysis.

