7.6.2 Third Islet Transplant Criteria

The option of a third islet transplant under this protocol will be considered only if all of the following conditions are met:

1. The subject received greater than 4,000 IEq/kg following the second transplant, but remains dependent on insulin for longer than one month after the second transplant.
2. There is evidence of partial islet graft function at one month.
3. The Protocol Chair, and the Site Principal Investigators (PIs), determined that there were no relevant protocol deviations at the site.
4. The subject has been compliant with study monitoring and prescribed immunosuppressive therapy.
5. No evidence of a serious and life-threatening infection, AE, or other condition that precludes attempting an intraportal injection or continuation of the post-transplant treatment regimen.
6. Subject has no unresolved SAEs.
7. No evidence of PTLD, requiring complete withdrawal from immunosuppressive therapy.
8. No evidence of hypersensitization, allergic responses, or other potentially serious drug reactions to medications required by the protocol.
9. Stable renal function as defined as being a creatinine of no more than one third greater than the average creatinine determination performed in the 3 previous months, until rejection, obstruction or infection is ruled out.
10. Absence of anti-HLA antibodies directed to the kidney transplant or to the current islet preparation detected by Luminex Single Antigen/specificity bead assay (including weakly reactive antibodies that would not be detected by a flow cross-match). All kidney and currently-proposed islet preparation donor specificities must be avoided in 2nd and 3rd islet transplants.

Subjects who have completed 8 months follow-up post-initial transplant will no longer be eligible for additional islet transplants funded under this protocol.

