APPENDIX 2: Reduced Follow-up Schedule of Events

Subjects prematurely discontinued from study treatment according to the criteria previously stated will remain in the study until normal termination. For the purpose of monitoring safety and efficacy parameters, the subjects should be followed according to the reduced follow-up schedule. The day on which the study treatment is discontinued is considered "Day 0". The last reduced follow-up visit will vary depending on when the subject discontinues study treatment and should be done at 3 years after the subject's final transplant.

Days post-discontinuation of study treatment	28	56	75	180	270	365	1 year post- final	2 years post- final	3 years post- final
Visit Windows (specified in days)	± 7						± 14		
Equivalent Month	1	2	2.5	6	9	12	Varies	Varies	Varies
ASSESSMENTS FOR ALL SUBJECTS ON REDUCED FOLLOW-UP									
Assess SAEs and hypoglycemic events ¹	X	X	X	X	X	X	X	X	X
Alloantibody (central)				X			X	X	X
HbA1c (central)							X	X	X
SCr (central)							X	X	X
QOL questionnaires via mail							X	X	X

1: If subject does not come to the study site for the visit, attempt to obtain information via a phone contact.

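### Section 7.6 sends partial-function subjects who miss a re-transplant criterion to reduced follow-up, against 5.8, 7.5 and Appendix 1; criterion 1 of 7.6.1 contradicts the planned first dose

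*Combined protocol and SAP*

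**What the plan says.** Five places in the combined protocol and SAP decide who leaves the full schedule of Appendix 1 for the reduced one of Appendix 2.

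- Section 7.6: "Subjects who do not meet criteria for a subsequent transplant will enter a reduced follow-up schedule (Appendix 2". Graft status is not mentioned.
- Section 5.8.2, under graft failure: "If/when it is determined that a subject will not receive a subsequent islet transplant, the subject will move to the reduced follow-up schedule".
- Section 5.8.3 lists five reasons for stopping study treatment early and sends those subjects to Appendix 2. Being ineligible for another infusion is not among them.
- Section 7.5, on recipients in general: "Please refer to the Appendix 1, SOE, for the clinical time points of specific follow-up study procedures". Footnote 3 of Appendix 1 applies that schedule after the first, second and third transplant.
- Appendix 2 describes its own population: "Subjects prematurely discontinued from study treatment according to the criteria previously stated will remain in the study until normal termination". It counts days from the date of discontinuation.

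The key secondary endpoint (section 4.1.2) is insulin independence at 1 and 2 years after the first and last infusion. The Study Definitions require an HbA1c, a fasting serum glucose and an MMTT within the visit window. They also require that "7 consecutive days of blood sugar and insulin readings are documented" close to it.

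On dose, section 4 sets a goal above 5,000 IEq/kg for the first transplant and section 5.2.1 a supplied dose of at least 5,000. Criterion 1 of section 7.6.1, in the text as read from the PDF, admits to a second transplant only subjects who received 5,000 IEq/kg or less and did not reach or keep independence.

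**The concern.** A site with a partial-function subject who cannot be re-infused has two conflicting instructions. Under 7.5 and Appendix 1 it continues the full metabolic testing. Under 7.6 it switches to a schedule with almost none.

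Several criteria in 7.6.1 are transient: an unresolved SAE (item 4), a creatinine rise still being worked up (item 7), or antibodies against the islet preparation on offer (item 9). None of these means that the graft has stopped working, yet 7.6 makes no distinction. If sites resolve the conflict differently, the 1- and 2-year metabolic data will be missing in a pattern tied to graft status and clinical course. That matters in a 20-subject comparison with an external control group.

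The dose criterion is a separate problem. Section 4 encourages centers to re-infuse subjects with partial function, but the criterion as written would turn away nearly all of those dosed as planned.

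**Working it through.** No planned figure bears on this point. The power calculation in section 10.3.1 concerns day 75 only. The check is therefore a comparison of clauses, with a little arithmetic.

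**Step 1. Who is sent where.**

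| Place | Subject | Schedule |
|---|---|---|
| 5.8.2 | Graft failure, no further transplant | Appendix 2 |
| 5.8.3 and Appendix 2 | Study treatment discontinued | Appendix 2 |
| 7.5 and Appendix 1, footnote 3 | Recipient after any transplant | Appendix 1 |
| 7.6 | Does not meet re-transplant criteria | Appendix 2 |

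For a failed graft with no further transplant, 7.6 and 5.8.2 agree. Section 7.6.1 considers only partial-function and failed grafts for re-infusion, so the remaining conflict concerns partial function. A subject who is merely ineligible has no discontinuation date, so the Appendix 2 clock has no starting point.

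**Step 2. What such a subject loses.** Appendix 2 schedules SAEs and hypoglycemic events, alloantibody, HbA1c, serum creatinine and quality-of-life questionnaires. Its HbA1c is timed only by years after the final transplant.

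| Assessment | Secondary use (4.1.2) | Appendix 1 | Appendix 2 |
|---|---|---|---|
| MMTT glucose and c-peptide | MMTT comparison; independence definition | yes | no |
| FSIGT | Engrafted islet mass | yes | no |
| Clarke score | Change from baseline | yes | no |
| CGMS | Glucose variability, hypoglycemia duration | yes | no |

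Without an MMTT the independence definition cannot be met on paper, whatever the subject's true state.

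**Step 3. Effect on the independence proportion.** With 20 transplanted subjects, each truly independent subject who is recorded as dependent lowers the observed proportion by 1/20 = 0.05, or 5 percentage points. A subject who stays at partial function changes it by 0. The 5 points need a subject who is ineligible for re-infusion, becomes independent without it, and is classed as dependent for want of a test. The documents give no count of such subjects.

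**Step 4. Dose criterion.** Let d be the first dose in IEq/kg.

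- Criterion 1 of 7.6.1 as read: d ≤ 5,000.
- Section 4 goal: d > 5,000. The overlap is empty.
- Section 5.2.1 supplied dose: d ≥ 5,000. The overlap is the single value d = 5,000.

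The parallel criterion for a third transplant (7.6.2, item 1) requires more than 4,000 IEq/kg at the second, again followed by failure to come off insulin. That structure describes an adequate dose that did not suffice, and points to ≥ in 7.6.1 as well.

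**The case against.** The strongest reply is that 7.6 is a loosely worded exception to the general pointer in 7.5, and that much of the text agrees with it. Section 5.8.2 matches it for failed grafts. The criteria that Appendix 2 refers back to could include those of 7.6. Appendix 2 also runs to 3 years after the final transplant, so the 36 months in 7.5 are respected. All of this stands. The conflict is about which assessments a partial-function subject receives, not about length of follow-up.

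Four stronger readings are tempting, and the documents do not support them.

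- *Every subject, including the insulin-independent, leaves Appendix 1 after 8 months.* A reader might infer this from section 7.6.2: "Subjects who have completed 8 months follow-up post-initial transplant will no longer be eligible for additional islet transplants funded under this protocol". But 7.6.1 considers only partial-function and failed grafts for a second transplant, the 8-month limit sits outside the numbered criteria, and the heading of 7.6 separates criteria from timing.
- *Appendix 2 is deficient because it has no 7-day glucose and insulin log.* Appendix 1 has no row for one either. Those records come from general requirements (sections 5.4.5, 5.7 and 9.1.1). The MMTT also supplies a basal glucose, so the missing MMTT is the main gap.
- *The day-75 result is at risk, because re-infusion is considered from day 30.* The Study Definitions excuse only subjects with graft failure from the day-75 metabolic assessments, so partial-function subjects are expected to complete them.
- *The 1- and 2-year analyses lose a stated amount of power.* The plan sets no decision rule for those times to which such a figure could apply.

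Two further objections hold in part. The Study Definitions class subjects who do not meet the criteria as dependent but do not say how to class a subject never tested, so the downward shift in Step 3 is an inference. Light follow-up after discontinuation under 5.8.3 is stated consistently. It can reach a subject with a working graft, since one listed reason is "An unexpected related SAE. The agent(s) to which the event is attributed will be discontinued", and the plan says "Data from these subjects will be used in the intent-to-treat analysis". That is a design choice, not a contradiction.

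The inequality in 7.6.1 is one machine-read symbol. If the source shows ≥, the dose point disappears. First doses below 5,000 are also not clearly impossible: section 4 calls its figure a goal, and Table 2 lists product from 4,000 IEq/kg.

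**Conclusion.** Two defects stand in the text as given.

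First, 7.6 is wider than 5.8.2, 5.8.3, 7.5 and Appendix 1 allow. On the likely reading it misroutes subjects with partial graft function who are ineligible for re-infusion. They lose the MMTT, FSIGT, Clarke and CGMS data used against CIT-06, and any later independence cannot be documented at 1 or 2 years. How many are affected cannot be derived. The effect on the independence proportion is 0 for those who stay at partial function, and 5 points for each truly independent subject counted as dependent. The primary endpoint at day 75 and the planned sample size are untouched.

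Second, criterion 1 of 7.6.1 contradicts the planned first dose and would bar nearly all subjects dosed as planned from a second infusion. This rests on the symbol being the same in the source PDF. The first defect does not depend on it.

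Both should be fixed. Neither undermines the trial's main comparison.

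**What to change.** (a) Reword 7.6 along these lines: *Subjects with confirmed graft failure who will not be re-transplanted, and subjects who discontinue study treatment under 5.8.3, enter Appendix 2. All other subjects with full or partial graft function stay on Appendix 1.* The columns of Appendix 1 end at Month 24 and day 730, so keep the visit at 3 years after the final transplant for these subjects to meet the 36 months in 7.5.

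(b) Check the symbol in criterion 1 of 7.6.1 against the source PDF. If it reads ≤, change it to ≥ 5,000 IEq/kg.

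The cost is one clause, one symbol and one retained visit. No new test is introduced, and sample size and power do not change. Offering the full independence assessments at 1 and 2 years to subjects who discontinue under 5.8.3 with a working graft would be a reasonable option, but it is an enhancement and not part of the correction.

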7.6.1 Second Islet Transplant Criteria

Islet transplant recipients with partial islet graft function (see Study Definitions) will be considered for a second islet transplant in the interim between 30 ± 3 days and 8 months post-initial infusion.

Islet transplant recipients with graft failure will be considered for a second islet transplant before 8 months post-initial infusion. Please refer to the MOP for details on this process, which includes review of the potency testing from the first transplant product and post-transplant clinical data.

In order to be eligible for a second islet transplant, the following requirements must be met:

1. Subject received \leq 5,000 IEq/kg with the first transplant, but failed to achieve or maintain insulin independence.
2. Subject has been compliant with study monitoring and prescribed immunosuppressive therapy.
3. No evidence of a serious and life-threatening infection, AE, or other condition that precludes attempting an intraportal injection or continuation of the post-transplant treatment regimen.
4. Subject has no unresolved SAEs.
5. No evidence of PTLD, requiring complete withdrawal from immunosuppressive therapy.
6. No evidence of hypersensitization, allergic responses, or other potentially serious drug reactions to medications required by the protocol.
7. Stable renal function as defined as being a creatinine of no more than one third greater than the average creatinine determination performed in the 3 previous months, until rejection, obstruction or infection is ruled out.
8. Absence of any medical condition that, in the opinion of the investigator, will interfere with a safe and successful second islet transplant.
9. Absence of anti-HLA antibodies directed to the kidney transplant or to the current islet preparation detected by Luminex Single Antigen/specificity bead assay (including weakly reactive antibodies that would not be detected by a flow cross-match). All kidney and currently-proposed islet preparation donor specificities must be avoided in 2nd and 3rd islet transplants.

If graft failure occurs after the second islet transplant, these recipients will be considered treatment failures and immunosuppression will be withdrawn.

